In the first dose-establishing study, 7 children (two given 250 mg niacin x 3 doses every 2 hours, 5 given 500 mg niacin x 3 doses every 2 hours) were screened and enrolled. In the second dose-establishing study, 5 children to be given 500 mg niacin x 4 doses every hour will be screened and enrolled. In the main study, up to 66 children will be screened for study entry and enrolled until the goal of 40 completed subjects, 20 for each group, is met. Children will be recruited from two sites, the Hatfield Clinical Center at the NIH in Maryland and Children's National Medical Center in Washington, DC; however, testing will be performed exclusively at the NIH.

We have chosen to pilot a randomized, double blind, placebo controlled trial in order to minimize the opportunity for bias in our study and maximize the interpretation of our results. We used a cross-over design to help eliminate potential of temporal factors related to giving niacin or placebo first. We consider this study a pilot to examine new methodology for growth hormone testing in obese children, and thus we did not choose to start with an unblinded smaller study first. We also did not want to expose subjects to the risks, however minimal, of a medication not approved for children under age 16y that requires IND filing without powering the study for the possibility of finding significant results.

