#### Main Study: Randomization

Only subjects meeting the inclusion and exclusion criteria during the screening visit will be randomized. Subjects will be assigned to receive placebo x 4 doses on the first day of GH stimulation testing and niacin 500 mg x 4 doses on the second day or they will be assigned to receive niacin 500 mg x 4 doses on the first day and placebo x 4 doses on the second day. Subjects

will be stratified by group and sex in blocks of 4 such that roughly equal numbers of subjects in each stratum will be assigned to each placebo and active medication administration order.

Additionally randomization of obese subjects will be stratified by BMI (95-99th percentile or >99th percentile).

Main Study: Inpatient evaluation:

Only subjects meeting the inclusion and exclusion criteria during the screening visit will be evaluated as inpatients. A total of 40 subjects in the two main groups will complete inpatient evaluation, although up to 50 may initiate inpatient evaluation in order to achieve full enrollment. The inpatient visit will occur within two months of screening visit to ensure consistency of physical exam and medical history throughout the study period. Patients will be admitted the night before the first day of testing. Additionally, literature suggests that several vitamins influence growth hormone secretion; thus, if applicable, vitamin supplements will be discontinued for three days prior to admission. All subjects will be admitted to the NIH Clinical Center for an evaluation that will include:

1. **Medical History and Physical Examination** with Tanner pubertal staging and anthropometric measurements including weight (in kg) and height (in cm) by stadiometer (3 repeated measures).
2. **DXA scanning** for determination of lean body mass and body fat mass.
3. **Placement of an intravenous line** to be used for medication administration and blood sampling over a 48 hour time period.
4. **Repeat urine pregnancy test** in girls age 10 and older.
5. **Overnight Fast** beginning at 10 pm on both nights; ending after completion of testing each day.
6. **Growth Hormone Stimulation testing** consisting of arginine (500 mg/kg IV up to maximum of 30 g, infused over 30 min) at 8:30am, followed by L-dopa (500 mg by mouth)

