**Monitoring subjects and criteria for withdrawal of subjects from study:**

The types, frequency, and duration of tests and visits are outlined on the flow diagrams at the end of this protocol document (Appendices B and C). Subjects will be examined at each of the two visits, which will be completed within a 2 month time period. If unanticipated toxicities are uncovered during the study, we will report these promptly to the IRB and FDA.

Subjects will be informed that they may withdraw from the study at any time.

Noncompliance with study procedures may lead to withdrawal of study subjects. Other events that will result in discontinuation of treatment include:

1. Inability to tolerate drug secondary to perceived or observed side effects.
2. Pregnancy.
3. Any verified abnormalities in laboratory values or physical status that cannot be explained by an intercurrent unrelated illness (or by obesity and insulin resistance itself)

that are considered WHO grade 2 or greater for gastrointestinal, hematologic, clinical hemorrhage, kidney/bladder, alopecia, pulmonary, cardiac, neurocerebellar, allergy, flu-like symptoms, metabolic, or eye toxicities; and grade 3 or greater for infection, anorexia, circulatory, neurologic, dermatologic, coagulation, endocrine, or performance status toxicities.

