### **Data Analysis**

Primary research outcome will be niacin-induced changes in arginine and L-dopa stimulated GH concentrations, measured as both area under the curve and peak values, in the overweight group compared with the control group. Secondary research outcomes will include changes in free fatty acid, glucose, and insulin concentrations during the GH stimulation tests. Since non-completion of the study is expected to be due to technical failures (e.g., nonfunctioning IVs) rather than subject factors, all analyses will be limited to subjects who complete both placebo and niacin studies. We do expect that some members of the control group will not reach a peak GH concentration of 7 ng/mL during the stimulation testing. We will report all control subjects in the final analyses. Analyses will be performed with age, Tanner stage, and initial BMI-SDS as covariates. Furthermore, tertiary analyses will also be performed to compare subjects in the Tanner I, Tanner II, and Tanner III groups to determine if any differences exist among these pubertal development stages. This analysis will be for exploratory purposes only; the study is not powered for this subgroup analysis. Additionally if any members of the control group have abnormally elevated lipid levels, we will specifically examine these subjects and their growth hormone concentrations. The primary outcome analysis will therefore be a repeated measures ANCOVA with subject group (obese and control) as the between factor, treatment (niacin or placebo) as the repeated measure, GH concentration (peak and AUC) as the outcome variables, and age, sex, and Tanner pubertal stage as covariates. We will also model the subject group by treatment interaction but no other interaction terms will be entered into the primary analysis.

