### **Determination of Sample Size**

Using data from the available studies that used acipimox, we performed power calculations based on the difference in effect on peak GH secretion found with and without use of acipimox in

obese adults. Following acipimox, this cohort showed an increase of 10.3 micrograms per liter in peak GH concentrations with a standard deviation of 6.1. Thus, at a power of .80 and an alpha of .05, the sample size necessary to detect a 10 microgram per liter difference in GH secretion is 14 in each group (e.g. obese versus control), and at a power of .95 and an alpha of .05, the sample size necessary to detect a 10 microgram per liter difference in GH secretion is 22 in each group. Given these calculations, we will aim for 20 subjects per group who complete all aspects of the study.

Allowing for 20% of subjects to fail to complete the main study for various reasons, the total number of subjects needed to be studied is 50 (25 in each group). We expect that we will need to screen no more than 66 children to find the 50 who meet the inclusion and exclusion criteria. Subjects will be randomized with the assistance of the NIH Investigational Drug Management and Research Section (IDMS); we anticipate sex and race/ethnicity to be similar in each study arm. For the pilot dose-finding studies, we will study no more than 5 per group (15 total) and screen at most an additional 10 subjects who do not qualify for these studies.

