6. **Niacin:** We successfully applied for FDA approval for the use of niacin in children under an investigational new drug application (IND) with [name], PhD as sponsor. Niacin is currently FDA-approved in the United States, but only for adults. Niacin has been used off-label to treat hyperlipidemia in children. A retrospective chart review of 21 children, age 4 to 14, found one subject who developed a febrile illness with elevation in serum aminotransferase who was discontinued off niacin after two months. Reversible adverse effects of niacin included flushing (71%), itching (19%), abdominal pain (14%), nausea (14%), vomiting (14%), headache (14%), and constipation (5%). 29% also demonstrated reversible dose-related elevations in AST concentrations. Niacin is known to cause transient skin flushing likely due to prostacyclin formation leading to cutaneous blood flow. In some trials testing GH secretion in adults, flushing has been observed after niacin

with rapid resolution. In the event of intolerable flushing as reported subjectively by the patient, we will administer a single dose of 10 mg/kg of ibuprofen to help alleviate the reaction. Nausea, vomiting, and temporary tightness of the chest have also been noted in some subjects. No other side effects have been noted in these studies; however, in uses of niacin to treat hyperlipidemia, the following other side effects have infrequently been reported: atrial arrhythmias, dental pain, liver injury, myalgia, myopathy, skin rashes, peptic ulcers, gastrointestinal bleeding as well as bleeding from other sites, diarrhea, onset of diabetes and worsening of diabetic control, infections, blurred vision and macular degeneration. Additionally the effects of niacin in pregnancy are unknown.

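### Completers-only analysis assumes technical dropout although treatment also stops for intolerance; nothing planned tests this, no safety population is set, and the main-study symptom form cannot separate niacin and placebo days

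*Combined protocol and SAP*

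**What the plan says.** **Analysis population.** After naming the GH, free fatty acid (FFA), glucose and insulin outcomes, the Data Analysis section says that "all analyses will be limited to subjects who complete both placebo and niacin studies". The reason given is that "non-completion of the study is expected to be due to technical failures (e.g., nonfunctioning IVs) rather than subject factors". The section plans no sensitivity analysis, no table of reasons for non-completion and no safety population.

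**Ways to become a non-completer.** Among the events that end treatment, the section on monitoring and withdrawal lists "Inability to tolerate drug secondary to perceived or observed side effects", along with graded toxicities. Determination of Sample Size makes its allowance in wider terms: "Allowing for 20% of subjects to fail to complete the main study for various reasons". The overview of the main study has children "enrolled until the goal of 40 completed subjects, 20 for each group, is met". Main Study: Inpatient evaluation adds "although up to 50 may initiate inpatient evaluation in order to achieve full enrollment". Non-completers are therefore replaced.

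**Tolerability.** The first item under Specific Hypotheses covers the fall in FFA and also the absence of significant adverse effects.

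**Safety data.** Adverse event reporting records all events. The data safety monitoring board (DSMB) reviews questionnaire data and side effects from all visits, in an A vs. B layout. The Monitoring Plan sends all events to annual review, and Appendix B schedules an adverse drug event assessment at the main-study admission. The Appendix D symptom form was hourly in the dose-establishing studies. In the main study it is given once, at the end of the stay.

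**The concern.** The completer rule rests on an expectation about why children drop out, and another section of the same protocol names a cause that is a subject and treatment factor. If children who tolerate niacin poorly are dropped and replaced, the GH and FFA results describe children who can take four doses, and a reader could not tell.

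Two further consequences concern tolerability. Children who stop because of niacin are the most informative ones for hypothesis 1, and the only population rule in the analysis section would leave them out. Also, a symptom form that pools the niacin day and the placebo day cannot by itself say which treatment a symptom followed. That weakens the A vs. B safety comparison and the check against the hourly expected rates on which the reporting waiver depends.

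**Working it through.** **1. The plan's own figure.** Completers wanted: 40 (20 per group). Non-completion allowed: 20%. Then 40 / (1 - 0.20) = 50 and 20 / (1 - 0.20) = 25 per group, as stated. The rule can therefore leave up to 10 of 50 starters, 5 per group if evenly split, out of every analysis.

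**2. Is the technical premise plausible?** Yes. The table of anticipated minor deviations expects 25% failure of intravenous access after two attempts, 25% missed venous samples and 10% loss of samples or data. These are deviation rates, not dropout rates, but they make technical loss a credible main cause.

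**3. Do the pilot data exclude dropout for intolerance?** No. Only 5 children received the main-study regimen. The documents report no discontinuation among them. If that means 0 of 5 (an assumption), the exact upper 97.5% bound is 1 - 0.025^(1/5) = 0.52. Those children reported 20-40% abdominal discomfort, nausea or emesis.

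**4. Possible bias in the GH contrast.** Let f be the share of a group's starters excluded for intolerance, and D the amount by which their niacin effect falls short of that of the completers. A group's mean effect is then shifted by f x D. With the same D in both groups, the obese-versus-control contrast is shifted by (f_obese - f_control) x D. The documents give neither f nor D; D is assumed to be 2.5 to 10 mcg/L.

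Standard error of the contrast with 20 completers per group:
- SD of change 6.1 (the sample-size section): 6.1 x sqrt(2/20) = 1.93.
- SD 6.1 x sqrt(2) = 8.63: 8.63 x sqrt(2/20) = 2.73.

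Both are shown because the plan does not say what its 6.1 measures. Used directly, 6.1 gives 7 and 11 per group by two-sided t-test, against the stated 14 and 22. An SD of 8.63 gives 13 and 21, which is close.

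| Extra children of 25 excluded for intolerance in one group | Shift, mcg/L | % of SE 1.93 | % of SE 2.73 |
|---|---|---|---|
| 0 | 0 | 0 | 0 |
| 1 | 0.1 to 0.4 | 5 to 21 | 4 to 15 |
| 2 | 0.2 to 0.8 | 10 to 41 | 7 to 29 |
| 5 (extreme) | 0.5 to 2.0 | 26 to 104 | 18 to 73 |

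The design difference is 10 mcg/L. Equal selection cancels in the contrast only if D is also equal. It does not cancel in the within-group hypotheses, where the shift is f x D.

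**5. Would a mixed model help?** Add children with a single evaluable day to the 20 completers per group (SD of change 6.1; within-child correlation 0.2, 0.5, 0.8, assumed). With 3 placebo-only and 2 niacin-only children per group, generalised least squares gives SE 1.84, 1.87 and 1.91, a gain of 1 to 5%. If all 5 stop on niacin, about half (2.5 expected under 1:1 order) are niacin-first and leave no evaluable day. With the remaining 2 or 3 placebo-only children, the SE is 1.88 to 1.92, a gain of 0.5 to 2.6%. The model assumes data missing at random, so it cannot rule out selection on tolerability.

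**6. The symptom form.** Niacin and placebo are given on consecutive days of one admission. The main-study form asks about the whole stay and records presence, duration and severity, with no day or onset field. Headache, flushing, nausea and vomiting are on the form. The risk section lists headache, nausea and vomiting for L-dopa and all four for arginine, and both drugs are given on both days. A ticked box cannot be assigned to niacin from the form alone. The waiver's expected rates are set by hour after niacin, which the form does not capture.

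**The case against.** **Safety lies outside the rule.** The completer sentence follows a list of hormonal and metabolic outcomes, and safety is handled elsewhere without a completer limit. A reader might infer that adverse events in non-completers are discarded. The documents do not support that: events are recorded for everyone and go to the DSMB and to annual review. What stands is narrower. Oversight review is not a planned summary for hypothesis 1, and the analysis section names no population for it.

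**Intolerance need not mean loss.** A response is planned "In the event of intolerable flushing as reported subjectively by the patient", so flushing need not end participation. In "A retrospective chart review of 21 children, age 4 to 14", one child was taken off niacin. Completion is also not defined, so a child who stops dosing but is still sampled might not be excluded. All of this stands, and it is why f is unknown.

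**The form is not the only source.** Staff record events as they occur, Appendix B schedules an assessment at the admission, and investigators review events manually. A reader might infer that no day-level safety data will exist. The documents do not show that; they show only that the form cannot supply them.

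**Biased GH results.** A reader might also infer that the GH results will be biased upwards. No document says that intolerant children respond less, so this is a possibility to be checked, not a finding.

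**Conclusion.** A minor point that holds. The analysis set rests on an expectation that may well be right, but the plan contains nothing that would show it. The size of any bias cannot be derived from the documents. Under the assumed D and small differences between groups it is 0.1 to 0.8 mcg/L, probably small beside the design difference of 10. Only the one-sided extreme approaches or reaches one standard error.

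Confidence is high that the plan has no disposition table, that the analysis section has no safety population, and that the main-study form lacks a day and an onset field. Nothing here questions the stopping criteria. Both-day completers remain a sensible primary set for a within-child comparison of GH.

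**What to change.** 1. Keep both-day completers for the GH, FFA, glucose and insulin analyses, state that the rule applies only to those outcomes, and define what counts as completing a test day.
2. For hypothesis 1, summarise adverse events and stops for intolerance by treatment day in every child given at least one dose.
3. Tabulate non-completion by reason, group, treatment order and day, including niacin-first children who leave no evaluable day.
4. Complete Appendix D once per test day, with an onset-hour field. This has to be arranged in advance, because the day of a symptom cannot be reliably recovered later from a whole-stay form.
5. Optional: fit the same repeated-measures model as a mixed model to all randomised children with at least one evaluable day, stating its missing-at-random assumption and its limits.

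Cost: some analysis wording, one or two tables and a second completion of a short form. No extra children, visits or samples are needed. The downside is a little more analysis work.

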### **Specific Hypotheses:**

In the course of this study we will test the following hypotheses:

- Inhibition of lipolysis by niacin will lead to a decrease in plasma FFA in obese and control children without inducing significant adverse effects.
- In the control group of short children (that are not found to be growth hormone deficient) peak stimulated GH concentration will be significantly greater than that observed in obese children. GH secretion of non-obese short children will be significantly augmented by niacin treatment.
- In obese children, peak stimulated GH concentration will be blunted after placebo but with niacin these measurements will increase significantly to achieve values similar to those seen in the non-GH-deficient control subjects after placebo.

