### **Study Design and Methods:**

#### Inclusion Criteria:

Subjects will qualify for the overweight group (for the dose-establishing studies 1 and 2 and main study) if they meet the following criteria:

1. Good general health.
2. Age  $\geq 7$  and  $< 15$  years.
3. Tanner stage I, II, or III for the breast among girls and testes  $< 10$  mL for boys based upon an examination by a trained physician or nurse practitioner.
4. Weight  $> 30$  kg.
5. Fasting plasma glucose  $< 100$  mg/dL, 2 hour post-dextrose glucose  $< 140$  mg/dL, and HgbA1C  $\leq 6.4\%$ .

6. Females who are age 10 or greater must have a negative pregnancy test.
7. Body mass index  $\geq$  95th percentile determined by Centers for Disease Control age and sex specific data (given that most pathology of obesity does not usually emerge until children cross the 95th percentile).
8. No evidence of growth failure as defined as height  $>$  5th percentile.

Subjects will qualify for the non-overweight control group (for the main study only) if they meet the following criteria:

1. Recommended by a pediatric endocrinologist to undergo GH stimulation testing to establish the diagnosis of GH-deficiency.
2. Good general health.
3. Age  $\geq$  7 and  $<$  15 years.
4. Tanner stage I, II, or III for the breast among girls and testes  $<$  10 mL for boys based upon an examination by a trained physician or nurse practitioner.
5. Weight  $>$  30 kg.
6. Fasting plasma glucose  $<$  100 mg/dL, 2 hour post-dextrose glucose  $<$  140 mg/dL, and HgbA1C  $\leq$  6.4%.
7. Females who are age 10 or greater must have a negative pregnancy test.
8. Height  $<$  5th percentile.
9. BMI between the 5th and 85th percentiles determined by Centers for Disease Control age and sex specific data.
10. Birth weight and length not consistent with small for gestational age (SGA) criteria or a history of intrauterine growth restriction (IUGR) based on recall history.

Exclusion criteria (for the dose-establishing studies 1 and 2 and the main study):

Subjects will be excluded if they have any of the following:

1. Baseline creatinine  $\geq$  1.0 mg/dl.

2. Significant cardiac or pulmonary disease likely to or resulting in hypoxia or decreased perfusion.
3. Hepatic disease with elevated liver function tests (ALT or AST)  $\geq 1.5$  the upper limits of normal.
4. Pregnancy.

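### The Data Analysis section gives two conflicting covariate lists; the one with BMI-SDS would be nearly collinear with study group in obese-versus-control comparisons of levels or change scores, though not in the primary group-by-treatment contrast

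*Combined protocol and SAP*

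**What the plan says.** Three parts of the combined protocol and SAP bear on this.

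- **Data Analysis, general sentence:** "Analyses will be performed with age, Tanner stage, and initial BMI-SDS as covariates". It is not limited to one outcome, one group or one model.
- **Data Analysis, primary model:** a repeated measures ANCOVA on peak GH and AUC, with group between subjects, treatment within subjects, "and age, sex, and Tanner pubertal stage as covariates". On interactions it says "We will also model the subject group by treatment interaction but no other interaction terms will be entered into the primary analysis". The primary outcome is "niacin-induced changes in arginine and L-dopa stimulated GH concentrations", compared between the overweight and control groups. The secondary outcomes (changes in FFA, glucose and insulin) have no model of their own.
- **Inclusion Criteria:** obese children have a BMI at or above the 95th percentile. For controls the rule is "BMI between the 5 th and 85 th percentiles determined by Centers for Disease Control age and sex specific data".

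Specific Hypotheses also contains comparisons of GH level between groups. In non-deficient short controls, "peak stimulated GH concentration will be significantly greater than that observed in obese children"; and obese children given niacin are expected to reach values like those of controls given placebo.

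**The concern.** The two lists differ in two items: the general one has BMI-SDS and lacks sex, and the primary one has sex and lacks BMI-SDS. An analyst could follow either for the analyses that have no model of their own.

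BMI-SDS is close to a continuous version of the group label, because no eligible child lies between the 85th and 95th percentiles. With both terms in a between-subject model, the group coefficient estimates the obese-control difference at a common BMI-SDS. No enrolled pair of children can show that difference directly. The Introduction reports that GH falls as BMI rises, so the covariate can be expected to take up much of the difference the trial attributes to obesity. A null or reversed adjusted group effect could then not be interpreted.

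At stake are the level comparisons in Specific Hypotheses and any change-score analysis of the secondary outcomes.

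**Working it through.** The documents state no standard-error inflation for this, so there is no figure to reproduce.

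**Inputs from the documents.** 20 completers per group (Determination of Sample Size). BMI cut-offs (Inclusion Criteria), converted to z-scores: 5th = −1.645, 85th = 1.036, 95th = 1.645. No upper BMI limit is set for the obese group, and no BMI-SDS means or SDs are given, so the distributions below are assumptions.

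**Step 1: inflation for a between-subject group term.** With equal groups, R² = (d/2)² / [(d/2)² + W]. Here d is the difference in mean BMI-SDS and W is the average within-group variance. The variance inflation factor (VIF) is 1/(1 − R²), and the standard error is multiplied by √VIF.

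Worked case: controls uniform on −1.645 to 1.036 (mean −0.304, SD 0.774) and obese uniform on 1.645 to 3 (mean 2.322, SD 0.391).
- d = 2.626, so (d/2)² = 1.725
- W = (0.599 + 0.153)/2 = 0.376
- R² = 1.725/2.101 = 0.821
- VIF = 5.59; √5.59 = 2.36

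| Controls (assumed) | Obese (assumed) | R² | VIF | SE ratio |
|---|---|---|---|---|
| uniform, 5th–85th | standard normal above 1.645 | 0.792 | 4.80 | 2.19 |
| uniform, 5th–85th | uniform 1.645–3 | 0.821 | 5.59 | 2.36 |
| standard normal cut to 5th–85th | uniform 1.645–3 | 0.834 | 6.04 | 2.46 |
| normal (−0.5, 0.7) cut to 5th–85th | mean 2.3, SD 0.3 | 0.894 | 9.46 | 3.08 |

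The first and last rows are the extremes of 28 pairs of assumed distributions: R² 0.79–0.89, VIF 4.8–9.5, SE ratio 2.2–3.1. Drawing samples of 20 + 20 under three such assumptions gave median VIFs of 5.7, 6.2 and 7.1 (SE ratios 2.39, 2.50, 2.67). The formula holds residual variance fixed; any variance that BMI-SDS explains would offset part of the inflation.

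**Step 2: what happens to the estimate.** This used 1,000 simulated trials of 20 per group with the worked-case distributions. Assumed values: GH slope −3 per BMI-SDS unit, between-child SD 5, within-child SD 4, niacin effect 5 in controls and 10 in obese children.
- Group difference in mean GH level: −5.31 (SE 1.90) without BMI-SDS, +2.60 (SE 4.43) with it. The sign changes, and the SE ratio is 4.43/1.90 = 2.33.
- Group difference in change score: 5.01 (SE 1.77) without BMI-SDS, 4.77 (SE 4.34) with it. The SE ratio is 4.34/1.77 = 2.45.

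**Step 3: the primary contrast.** Write each child's GH as a group term, a treatment term, group × treatment, a BMI-SDS main effect and a child effect. Data Analysis restricts the analysis to children who complete both days. In the niacin-minus-placebo difference the BMI-SDS main effect therefore subtracts out. A mixed model fitted to one simulated data set confirms it:
- group × treatment without BMI-SDS: 4.82 (SE 1.745)
- with a BMI-SDS main effect: 4.82 (SE 1.745), ratio 1.00
- with BMI-SDS × treatment added: −4.16 (SE 4.898), ratio 4.898/1.745 = 2.81

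The plan excludes the third model from the primary analysis.

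**The case against.** The strongest defence is that the specific sentence should govern. The primary ANCOVA has its own list, without BMI-SDS. The group term of that model gives the obese-control level comparison, and the obese-on-niacin versus control-on-placebo comparison can come from the same fit. No separate level analysis with BMI-SDS is described. The secondary outcomes might use the same repeated-measures structure, in which case a main-effect covariate would cancel there too. The general sentence might also be meant for within-group work, since randomization of obese children is stratified by BMI.

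Much of this stands, and it rules out three readings that a reader might infer.
- **That the primary result is compromised.** It is not. The specified model omits BMI-SDS and bars other interactions, and Step 3 shows that a main effect would change nothing.
- **That adjustment removes the obese-control difference.** It redefines the difference and makes it imprecise; the adjusted value need not be zero.
- **That the inflation has a floor of about 2.4-fold.** That is a fair central value, but it depends on distributions the documents do not give, and plausible ones go down to about 2.2.

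The defence does not remove the conflict. The general sentence is unrestricted, and it is the only covariate rule that reaches analyses without a stated model. Nothing says it is confined to within-group use.

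**Conclusion.** The concern holds for a limited part of the plan. The two covariate lists conflict. Following the general one in a between-group comparison of levels or change scores would give a group effect defined at equal BMI-SDS, dependent on extrapolation, and with a standard error about 2.2 to 3.1 times larger. The size rests on assumed BMI-SDS distributions and on unchanged residual variance. The sign change in Step 2 also rests on the assumed slope and illustrates what can happen, not what will. Whether the secondary outcomes would be affected depends on a model the plan does not state. The primary group-by-treatment contrast is sound as specified on this point. This should be corrected, but it is not a threat to the main analysis.

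**What to change.** In Data Analysis, replace the two lists with one (age, sex, Tanner stage) for every model that contains subject group, and state that it applies to the GH level comparisons and to the FFA, glucose and insulin outcomes. Delete BMI-SDS from those models. Use BMI-SDS, or the DXA fat mass already collected under Main Study: Inpatient evaluation, only within the obese group, as a secondary analysis of how adiposity relates to GH and to the niacin-induced change. If a between-group model with BMI-SDS is still wanted, label it a sensitivity analysis and note the extrapolation. The cost is one sentence of the plan, with no new data and no burden on participants.
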